1.5 OVERALL SYNOPSIS OF THE CLINICAL INVESTIGATION

ANSM registration #:	2023-A01479-36
Clinical investigation plan #:	23E1077
Title of the clinical investigation:	SAFETY AND EFFECTIVENESS CLINICAL EVALUATION OF THE RANGE OF INJECTABLE MEDICAL DEVICES VISCOL IN AESTHETIC TREATMENT
Sponsor:	KYLANE LABORATOIRES SA [name] SWITZERLAND
Development phase	Exploratory study
Objectives:	
The primary objective is to evaluate the effectiveness of the VISCOL range used on different treated zones (facial and body areas) one month (M1) after treatment using clinical evaluation of the global aesthetic improvement (GAIS) rated by an independent investigator.
 
The secondary objectives of the study are to collect data for the VISCOL range on:
 
- the effectiveness of the range used on different treated zones four months (M4) after treatment using clinical evaluation of the global aesthetic improvement (GAIS) rated by an independent investigator.- the effectiveness on the improvement of facial skin quality by objective measurements of skin biomechanical parameters using Cutometer® and skin hydration using Moisturemeter® one (M1) and four (M4) months after treatment.- subject's satisfaction and subject's opinion on aesthetic improvement on the different treated zones using clinical evaluation of the GAIS at M1 and M4.- the injector's satisfaction on the injection quality using subjective evaluation questionnaire after injection on D0.- the safety using clinical evaluation of the Injection Site Reactions (ISR) rated by the subject and the investigator, and by collection of adverse events (AEs) at Day 0 (D0) one month (M1), four months (M4) and six months (M6). 
Another objective will be to illustrate the device effectiveness by realization of face and body macrophotographs.

Design:	◆ Open study, ◆ intra-individual, ◆ single dose, ◆ single centre.
Planned Sample Size:	86 subjects in total divided in 2 groups, according to the kind of treated zone: Group 1 (VISCOL Face): 64 subjects treated by VISCOL (one injection on D0) on both sides of the face in the following areas: malar and sub-malar areas (obligatory areas) and optional areas mandibular and/or chin. Group 2 (VISCOL Body): 22 subjects treated by VISCOL (one injection on D0) on both sides in the following areas: decolletage and neck areas (obligatory areas) and one optional area abdomen or internal face of the arm.

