Endpoints:	
Primary endpoint: Proportion of subjects having an improvement of the zone treated with the overall VISCOL range of devices as assessed by an independent investigator, one month (M1) after treatment, using the GAIS. An improvement is defined as a subject with "very much improved", "much improved" or "improved" score on the GAIS.
 
Secondary endpoints:
 
- Proportion of subjects having an improvement of the zone treated with the overall VISCOL range of devices as assessed by an independent investigator four months (M4) after treatment, using the GAIS.- Proportion of subjects having an improvement of the zone treated with each VISCOL device for the 2 groups independently as assessed by the independent investigator one month (M1) and four months (M4) after treatment, using the GAIS.- Proportion of subjects having an improvement of the zone treated with the VISCOL range of devices overall as assessed by the subjects, one month (M1) and four months (M4) after treatment, using the GAIS.- Proportion of subjects having an improvement of the zone treated with each VISCOL device for the 2 groups independently as assessed by the subjects, one month (M1) and four months (M4) after treatment, using the GAIS.- Change from baseline of facial skin hydration measured with Moisturmeter® one month (M1) and four months (M4) after treatment.- Change from baseline of facial skin biomechanical parameters measured with Cutometer® one month (M1) and four months (M4) after treatment.- Patient's satisfaction on the treatment outcomes using a subjective evaluation questionnaire completed at one month (M1) and four months (M4) after treatment.- Injector's satisfaction on the injection quality using a subjective evaluation questionnaire completed immediately after injection on D0.- The safety of the VISCOL range and of each VISCOL device independently will be assessed by:
• collection of immediate and early Injection Site Reactions (ISRs) by the subjects on a daily-log every day up to one month after treatment.• collection of immediate Injection Site Reactions (ISRs) by the injector immediately after treatment.• collection of ISRs by the independent investigator one month (M1) and four months (M4) after treatment.• collection of AEs throughout the study. 
Illustration of the treatment effect one month (M1) and four months (M4) after treatment compared to baseline by photographs taking.

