
Study Procedures:	Screening, D0, D7 (phone call for safety), M1, M4, M6 (phone call for safety)
Statistical methods:	
The statistical analysis will be performed by the CRO biostatistician.
 
The analysis of the primary performance parameter will be performed on the ITT and PP population as sensitivity analysis. The conclusion of the primary performance parameter will be performed on the ITT population.
 
The analysis of the secondary effectiveness parameters will be performed on the ITT and PP population. In case the ITT and PP population differ by less than 10%, only the PP population will be analyzed.
 
The analysis of the safety/tolerance parameters will be performed on the "safety" population.
 
A descriptive analysis of the population will be performed, including subject's characteristics, subject's disposition, deviations to the protocol, injections characteristics.
 
For the primary evaluation criteria:
 
Descriptive statistics:
 
For the parameter GAIS investigator with the 5 level scores (at M1 and M4), the frequencies and percentages will be presented for the overall face and body score and for the scores by product (separated by the 4 zones: "face", "decolletage and neck", "area abdomen" and "arm").
 
A two derived parameter will be defined based on the parameters GAIS subject and investigator as a score of 2 levels (1=Improvement (Very much improved, Much improved and Improved) and 2=No change or worsening). At each time point, these parameters will be described in frequencies, percentages and IC95% for the overall face and body score and for the scores by product (separated by the 4 zones: "face", "decolletage and neck", "area abdomen" and "arm").
 
• For group 1 : if GAIS value on face is "Very much improved", "Much improved" or "Improved" then the subject is responder (Responder='Yes') Else the subject is not responder (Responder='No')• For group 2 : if GAIS value on "decolletage and neck" is "Very much improved", "Much improved" or "Improved" then the subject is responder (Responder='Yes') Else the subject is not responder (Responder='No') 
Inferential analysis for the primary evaluation criterion
 
For the derived outcome responder rate at M1 (1 month after injection) for the GAIS Investigator, a binomial exact test (bilateral approach) vs 60% will be applied for the overall score. This test will compare the proportion of improvement to 60%.

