
	
In addition, a sensitivity analysis will be performed on a global binary variable based on both GAIS scores, assessed by the investigator and by the subject. If the subject is considered as improved by both scores, then the outcome will be "Improved" else the outcome will be "Not improved". This composite parameter will be summarized in frequency and percentage and presented associated with its 95% CI, by time-point for the overall face and body scores and by product (separated by the 4 zones: "face", "decolletage and neck", "area abdomen" and "arm").
 
For the secondary evaluation criteria:
 
GAIS subject : For the parameter GAIS subject with the 5 level scores (at M1 and M4), the frequencies and percentages will be presented for the overall face and body scores and for the scores by product (separated by the 4 zones: "face", "decolletage and neck", "area abdomen" and "arm").
 
Biometrological parameters: All the parameters measured with Cutometer® and Moisturemeter® will be summarized using the descriptive statistics for quantitative data for each time point (D0, M1, M4). For each parameter, a two-tailed paired t-test will be carried out to assess whether each time point after injection (M1, M4) differ significantly from the baseline value (D0).
 
Subjective questionnaire statistical analysis: The distribution of each item of the injector and subject questionnaires will be described in frequencies and percentages. For each item of the subject questionnaire, the percentage of subject satisfied, (percentages of answers "totally agree", "agree") will be computed and described in frequencies and percentages. For each item of the injector questionnaire, the percentage of answers "satisfied" or "very satisfied" will be computed and described in frequencies and percentages.
 
Safety analysis: - The injection site reactions parameters assessed by the investigator and the subject will be described. - The individual listing of AE will be provided. AE/ADE will be summarized by product. AE/ADE will be further tabulated by seriousness, severity and relationship to the investigational device and procedure.

Estimated dates of the study:	Clinical investigation beginning: Q4 2023 Clinical investigation end: Q3 2024 Expected recruitment period duration: 4 months. Clinical investigation overall duration: 6 months + recruitment period Duration by subject: 6 months + screening period

FLOW-CHART

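### Do unadjusted paired t-tests on every skin parameter at two visits undermine the skin-quality findings?

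*Combined protocol and SAP*

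**What the plan says.** All references are to section 1.5, the overall synopsis, of the combined protocol and SAP.

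- **Objectives.** One secondary objective concerns "the effectiveness on the improvement of facial skin quality by objective measurements of skin biomechanical parameters using Cutometer" and skin hydration, at M1 and M4. The secondary objectives as a group are framed as data collection.
- **Endpoints.** Two separate secondary endpoints cover this: "Change from baseline of facial skin hydration measured with Moisturmeter® one month (M1) and four months (M4) after treatment" and "Change from baseline of facial skin biomechanical parameters measured with Cutometer® one month (M1) and four months (M4) after treatment". The biomechanical parameters are plural but neither counted nor named.
- **Statistical methods, Biometrological parameters.** "All the parameters measured with Cutometer® and Moisturemeter® will be summarized" at D0, M1 and M4. Then: "For each parameter, a two-tailed paired t-test will be carried out to assess whether each time point after injection (M1, M4) differ significantly" from D0. No significance level, order of testing or adjustment is stated.
- **Statistical methods, primary criterion.** The one other significance test described is for the investigator-rated GAIS responder rate at M1: "a binomial exact test (bilateral approach) vs 60% will be applied for the overall score". A rule on which population carries the conclusion is given for this parameter only (ITT).
- **Flow-chart and Planned Sample Size.** The instruments are used in the face group alone: "Group 1 (VISCOL Face): 64 subjects treated by VISCOL".
- **Development phase.** The study is labelled exploratory.

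**The concern.** One objective, better facial skin quality, is served by an open-ended set of tests: every Cutometer parameter plus hydration, each at two visits. No parameter or visit is the main one, and nothing says how many significant results, or which, would count in favour of the objective. If any single significant result were enough, the real error rate behind a skin-quality statement would be several times the nominal level.

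The point has some weight because these are the only significance tests besides the primary, and they are the objective measurements in an open study whose other effectiveness outcomes are ratings. A lone significant parameter could be quoted as support when it is noise.

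**Working it through.** The plan states no error rate or number of tests here, so there is no figure of its own to reproduce.

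**Inputs**

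- Parameters, k: at least 2 from the Cutometer (plural in Endpoints) plus 1 for hydration, so k ≥ 3. Larger values are assumptions.
- Tests: M1 and M4 each against D0, so m = 2k ≥ 6.
- Level per test: not stated; 0.05 two-sided is assumed.
- Subjects: 64 (face group).

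**Independent tests.** The chance of at least one false positive is 1 − 0.95^m.

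| k | m | Chance | Expected false positives (0.05 × m) |
|---|---|---|---|
| 3 | 6 | 26.5% | 0.3 |
| 5 | 10 | 40.1% | 0.5 |
| 7 | 14 | 51.2% | 0.7 |
| 10 | 20 | 64.2% | 1.0 |

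At m = 13 the result is 1 − 0.95^13 = 48.7%, so 14 is the smallest number of independent tests that passes 50%. Because m is even, that means k ≥ 7.

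**Correlated tests.** Independence is not realistic. The M1 and M4 changes subtract the same D0 value. If the three measurements have equal variance σ² and equal correlation ρ, the two changes have covariance σ²(1 − ρ) and variance 2σ²(1 − ρ) each, so their correlation is 0.5. Parameters read from one instrument should also be correlated. Paired t-tests were simulated with 64 subjects, 6,000 replicates, no true change, and correlation 0.5 between the two visits' changes:

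| k | Between-parameter correlation 0 | 0.5 | 0.8 |
|---|---|---|---|
| 3 | 24.5% | 22.6% | 17.9% |
| 5 | 38.3% | 30.3% | 22.6% |
| 7 | 48.2% | 37.7% | 26.4% |
| 10 | 60.9% | 47.6% | 29.8% |
| 15 | 75.9% | 57.0% | 36.0% |

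With a between-parameter correlation of 0.5, the chance is still below 50% at ten parameters.

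**Direction.** The objective is improvement, and a false result supports it only in the favourable direction, at 0.025 per test. Under independence, 1 − 0.975^m gives 14.1%, 22.4% and 29.8% for m = 6, 10 and 14.

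**What adjustment would do.** Bonferroni at m = 6 uses 0.05/6 = 0.0083 per test and gives 1 − (1 − 0.0083)^6 = 4.9%. It works arithmetically, at the price of a stricter threshold for every real change.

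**The case for a change.** The strongest case for a change is that an exploratory label is not a rule of interpretation. The plan speaks of significant differences without attaching a level. It chose inference for the instrument data while leaving subject GAIS, the questionnaires and safety descriptive. It also allows secondary effectiveness to be analysed on ITT and PP, or on PP alone when the two differ by less than 10%. Naming hydration and one Cutometer parameter, and testing them with Holm or in a fixed sequence, would need no new data.

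Part of this stands. The parameter list, the level and the status of the p-values are not written down, and the family-wise error is above 5% on any reasonable reading. The rest does not force a change:

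- A rule that any one significant parameter establishes better skin quality appears nowhere in the plan; it has to be supplied by the reader.
- A confirmatory pair of secondary endpoints sits awkwardly in an exploratory study without an untreated comparator. Face subjects are also selected for dry skin (hydration below 60 UA on the Corneometer, inclusion criterion 5). Mean hydration could therefore drift upward after D0 with no treatment effect, to the extent that the two hydration devices agree. No alpha adjustment addresses that.
- The ITT and PP sets should overlap heavily, so a second run is not a fresh set of independent chances.

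**Conclusion.** The observation is correct but no change is needed. At an assumed 0.05 per test, the chance of at least one false significant change is about 18% to 26% for the six tests the wording implies at minimum. It rises with each added parameter and reaches 50% only at about 14 independent tests. These figures rest on an assumed level, an assumed parameter count above the minimum, and assumed correlations. The statement that no adjustment is made means only that none appears in the synopsis.

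The plan promises no family-wise error rate for these endpoints, so none is missed, and the primary conclusion is unaffected. Unadjusted p-values on secondary measurements in an exploratory study are a fair trade-off. What remains is detail that an analyst can sensibly fill in: report every parameter at both visits with its mean change and confidence interval, and read the p-values as descriptive. With all results shown, an isolated significant one can be weighed against the 0.3 false positives expected in six tests or the 0.7 in fourteen. The matter would be different only if a confirmatory skin-quality claim were to rest on these tests, and the documents do not say that one will.

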Procedure	Visit 1 Screening	Visit 2 Day 0	Phone call 1 Day 7	Visit 3 M1	Visit 4 M4	Phone call 2 M6
Days	D-x	D0	D7 ± 1	D30±4	D120±7	D180±7
Informed consent	●					
Medical examination to check inclusion and exclusion criteria	●					
Medical history and previous/ongoing treatment(s)	●					
Confirmation of eligibility	●	●				
Urinary pregnancy test for women of childbearing potential		● ^b				
Injection by injector		●				
ISR by the injector		● ^a				
Subjective evaluation questionnaire by the injector		● ^a				
Subjective evaluation questionnaire by the patient				●	●	
GAIS by an independent investigator				●	●	
GAIS by the subjects				●	●	
ISR by an independent investigator				●	●	
ISR by the subjects		● Each day during 1 month after injection, on the daily-log				
Group 1: Macrophotographs (full face + 2 profiles)		● ^b		●	●	
Group 1: Cutometer® + Moisturemeter®		● ^b		●	●	
Group 2: Macrophotographs of the treated zone(s)		● ^b		●	●	
Adherence control, record of AE, concomitant treatments	●	●	●	●	●	●
End of study form						●

a : after injection, b : before injection

AE: Adverse Event – GAIS: Global Aesthetic Improvement Scale- ISR: Injection Site Reaction

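### Hydration and Cutometer endpoints are changes from baseline, but no mean change or 95% CI is planned, and the M4 test has no protection if drop-out is related to the M1 result

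*Combined protocol and SAP*

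**What the plan says.** All references are to section 1.5 (overall synopsis) of the combined protocol and SAP.

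- **Endpoints, secondary.** Both instrumental endpoints are defined as changes: "Change from baseline of facial skin hydration measured with Moisturmeter® one month (M1) and four months (M4) after treatment" and "Change from baseline of facial skin biomechanical parameters measured with Cutometer® one month (M1) and four months (M4) after treatment".
- **Statistical methods, biometrological parameters.** The measurements "will be summarized using the descriptive statistics for quantitative data for each time point (D0, M1, M4"). The only inference is the paired test, with D0 as the reference: "For each parameter, a two-tailed paired t-test will be carried out to assess whether each time point after injection (M1, M4) differ significantly". No mean change, SD of change or confidence interval is named. For the GAIS proportions, the same section does ask for 95% intervals.
- **Statistical methods, analysis sets.** For secondary effectiveness, ITT and PP are both named, with this exception: "In case the ITT and PP population differ by less than 10%, only the PP population will be analyzed".
- **Who is measured.** The flow-chart row "Group 1: Cutometer® + Moisturemeter" marks D0 (before injection), M1 and M4. The planned number is in the sample-size row: "Group 1 (VISCOL Face): 64 subjects treated by VISCOL (one injection on D0) on both sides of the face".

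The synopsis gives no drop-out rate, no rule for missing values and no significance level for these endpoints.

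**The concern.** There are two separate gaps.

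**Reporting.** The endpoint is a change, while the listed outputs are levels by visit and a test result. A reader would learn whether the change is significant without its size or precision. In an open, uncontrolled study that the sponsor labels exploratory, size and precision are most of what these endpoints can offer. The visit summaries do not fill the gap. The interval for a paired change depends on the within-subject correlation, which visit means and SDs do not show. If some subjects miss M4, the D0 and M4 summaries also describe different people.

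**Drop-out.** Without imputation, a paired t-test at M4 drops everyone who lacks an M4 value. Those who attended M1 have a measured M1 change, which may predict what M4 would have shown, and the test does not use it. If subjects with a poor M1 result tend to skip M4, the mean M4 change is shifted towards improvement and the test rejects too often.

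**Working it through.** The synopsis states no effect size, SD or power for these endpoints, so there is no figure to reproduce. What follows is illustration. From the document: n = 64, with visits D0, M1 and M4. Assumed: two-sided 5% level, drop-out share, correlations and drop-out mechanism.

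**1. What the paired t-test covers.** It is t = mean change / (SD of change / √n), the one-sample test that the mean change is zero. The estimate and its standard error are therefore formed within the test. What is missing is an instruction to report them.

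**2. Precision that goes unreported.** The half-width of the 95% CI, in SDs of change, is t(0.975, n−1)/√n:
- 64 pairs: 1.998/8 = 0.25
- 57 pairs (10% missing): 2.003/7.550 = 0.27
- 51 pairs (20% missing): 2.009/7.141 = 0.28

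With equal visit SDs, SD of change = visit SD × √(2(1−r)). For 64 pairs the half-width is 1.183 × 0.25 = 0.30 visit SD at r = 0.3, and 0.447 × 0.25 = 0.11 at r = 0.9. The visit summaries cannot tell these cases apart.

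**3. Differencing visit means.** If a share d misses M4 and their baseline differs by b SD from that of subjects who stay, the M4 mean minus the all-subject D0 mean departs from the paired mean change by d × b. At d = 0.10 and b = 0.5 to 1, this is 0.05 to 0.10 SD.

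**4. Size of the M4 bias.** If the true mean change of those who stay exceeds that of those who leave by k SD, the mean among those who stay exceeds the all-subject mean by d × k. For k from 0.25 to 1, this is 0.025 to 0.10 SD at d = 0.10, and 0.05 to 0.20 SD at d = 0.20. It is zero if k = 0.

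**5. Simulation with drop-out driven by M1.** 64 subjects, no true M4 change, correlation 0.6 between M1 and M4 change. The log-odds of leaving rise by the slope shown for each SD of poorer M1 change. Rows for slopes 1 and 2 use 6,000 runs per setting. The slope 0.5 rows come from separate, smaller runs and are rounded; no model error rate is listed for them.

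| Drop-out | Slope | Bias of paired t-test (SD) | Its error rate | Error rate using M1 |
|---|---|---|---|---|
| 10% | 0.5 | about 0.03 | 5–7% | – |
| 10% | 1 | 0.054 | 7.2% | 5.1% |
| 10% | 2 | 0.081 | 9.5% | 4.8% |
| 20% | 0.5 | about 0.06 | 6–7% | – |
| 20% | 1 | 0.104 | 10.9% | 4.6% |
| 20% | 2 | 0.156 | 20.6% | 4.6% |

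The last column is the likelihood (regression) estimator that also uses M1; it shows no visible bias here. With slopes 1 to 2 and 10% drop-out, the paired test's error rate is 5.5–6.4% at correlation 0.3 and 8.4–14.4% at 0.8. At 5% drop-out it stays between 4.9% and 7.5%. With no or random drop-out, both methods are valid.

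**6. Drop-out driven by the M4 value itself.** The M1-based estimate is then biased too: 0.06 to 0.09 SD with 7–12% error at 10% drop-out, and 0.11 to 0.18 SD with 14–31% error at 20%. The paired t-test is further off.

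**7. The 10% rule.** The base of the percentage is not stated. On 64 subjects, up to 6 exclusions (6/64 = 9.4%) lead to PP only; on 86, up to 8 (8/86 = 9.3%).

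**The case against.** **The change is tested.** A reader might infer that the plan does not estimate the change at all. The documents do not support that: the paired t-test matches the endpoint, and the mean change is computed within it. The gap is in what is specified for reporting.

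**This is a synopsis.** The phrase about descriptive statistics for quantitative data does not list them and does not rule out a column for the change. That is fair. But the section does name 95% intervals for GAIS, so naming one here would be consistent and easy.

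**Restriction to subjects with both values is inferred.** The plan does not say so; it follows from a paired test with no stated imputation. This stands as a limit on the wording.

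**The bias is hypothetical, and the larger figures need a steep mechanism.** Slopes of 1 to 2 multiply the odds of leaving by 2.7 to 7.4 per SD of poorer M1 change, and no document supports that or the correlation of 0.6. If leaving depends instead on a perceived result correlated only 0.3 with the instrument's M1 change, slopes of 1 to 2 give 0.01–0.03 SD and about 5% error at 10% drop-out, and 0.03–0.05 SD and 6–6.5% at 20%. This stands: the 21% figure is the extreme corner of the grid.

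**A model using M1 is not a cure.** It removes the bias only when drop-out depends on observed values. This also stands, although it was never materially worse than the paired test in the settings tried.

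**The endpoints are secondary.** The primary conclusion rests on investigator GAIS at M1 and is untouched.

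**Conclusion.** The point holds in limited form. No mean change and no 95% CI are planned for two endpoints defined as changes, and no handling of missing values is stated. The reporting gap exists even with complete data.

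The M4 bias is a conditional risk. Under the assumptions in the working (64 subjects, correlation 0.6, slopes 0.5 to 2), it is about 0.03–0.08 SD with a 5–10% error rate at 10% drop-out, and 0.06–0.16 SD with 7–21% at 20%. A reader might infer that the M4 result will be biased. The documents do not support that, because they give neither a drop-out rate nor any reason to expect drop-out related to the M1 result.

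The PP rule adds to the concern. It can remove the ITT analysis of these endpoints altogether, whereas the primary endpoint is concluded on ITT. The change is worth making because it uses data already collected and costs little.

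**What to change.** For each Cutometer and Moisturemeter parameter, specify in the SAP:

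1. One repeated-measures model for the D0, M1 and M4 values, with visit as a factor and unstructured covariance, in all Group 1 subjects with a D0 value. Run it whatever the outcome of the 10% PP rule, and say so, because that rule would otherwise override it.
2. Mean change from D0 to M1 and from D0 to M4, each with a 95% CI, as the reported result.
3. The paired t-test as a check, with its own mean change and CI in the same subjects.
4. The number of subjects with a value at each visit, and a statement that the model assumes values are missing at random. If drop-out depends on the unseen M4 value, the model reduces the bias but does not remove it.

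With complete data, the model and the paired analysis give the same mean change and, with matching degrees of freedom, the same interval. The cost is SAP wording, a short program and one stated assumption. No new data or visits are needed.

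### Do the Group 1 Moisturemeter and Cutometer tests against D0 need an untreated reference site?

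*Combined protocol and SAP*

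**What the plan says.** All references are to section 1.5, the overall synopsis, and its flow-chart.

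- **Objectives.** The secondary objectives open with "The secondary objectives of the study are to collect data for the VISCOL range on". One of them is "the effectiveness on the improvement of facial skin quality by objective measurements of skin biomechanical parameters", together with hydration. The development phase is given as exploratory, and the design as open, intra-individual and single-centre.
- **Planned Sample Size.** Group 1 has "64 subjects treated by VISCOL (one injection on D0) on both sides of the face in the following areas" that the protocol lists, so there is no untreated side.
- **Endpoints.** Hydration is defined as "Change from baseline of facial skin hydration measured with Moisturmeter® one month (M1) and four months (M4) after treatment". The Cutometer endpoint has the same form.
- **Statistical methods.** "The analysis of the secondary effectiveness parameters will be performed on the ITT and PP population". For the instrument readings, "a two-tailed paired t-test will be carried out to assess whether each time point after injection (M1, M4) differ significantly from the baseline value", in addition to descriptive statistics at D0, M1 and M4.
- **Flow-chart.** The row "Group 1: Cutometer® + Moisturemeter" has entries at D0 before injection, M1 and M4. There is no row for a reference site.
- **Estimated dates.** The start is Q4 2023. For the rest, "Clinical investigation end: Q3 2024 Expected recruitment period duration: 4 months".

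**The concern.** The objective and the analysis heading both speak of effectiveness, yet the null hypothesis of the paired test is zero mean change over time, not zero device effect. Anything that moves all subjects the same way between D0 and a later visit, such as season or instrument drift, is part of the tested mean. The exclusions on medication, intensive sun exposure and changed life habits, and the stable-weight criterion, remove some of these sources but not all.

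These are also the only secondary endpoints for which the synopsis plans a hypothesis test, so they will carry p-values. M4 lies about a third of a year after D0. A significant M4 result could be credited to the device when part or all of it is a time trend, or an opposite trend could hide a real effect. The planned readings could not tell these cases apart.

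**Working it through.** **Inputs.** From the documents: n = 64; two-sided paired t-test; visits at days 30 and 120; start in Q4 2023, end in Q3 2024, 4 months of recruitment, 6 months per subject. Assumed, because the documents do not give them: alpha 0.05; an annual cosine with its trough between 1 January and 1 February; D0 dates spread evenly over 122 days; amplitude expressed in SDs of the within-subject change; the gap from screening to D0 ignored. The documents give no effect size, SD or power for these tests, so there is no stated figure to reproduce.

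**Does the test match the endpoint?** The endpoint is change from baseline at M1 and M4. The test compares M1 and M4 with D0. They match, and the test is valid for that quantity.

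**Sensitivity to any shared drift.** The result is significant once the observed mean change reaches t(0.975, 63)/√64 = 1.998/8 = 0.25 SD, whatever the cause. By noncentral t (63 df), a true drift of 0.1, 0.2 or 0.3 SD with no device effect gives p<0.05 in 12%, 35% or 66% of trials.

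**Calendar.** 4 + 6 = 10 months. To begin in Q4 2023 and finish by the end of Q3 2024, the start must lie between 1 October and about 30 November 2023.

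**Seasonal shift.** For an annual cosine of amplitude 1, the mean shift k days after D0 is

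2 sin(πk/365.25) × [sin(u)/u] × sin(2π(m + k/2)/365.25),

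where u = 122π/365.25 and m is the number of days from the trough to mid-enrolment (start + 61 days). The factor sin(u)/u is 0.826. The multiplier of the last sine is 1.717 × 0.826 = 1.42 at M4 and 0.510 × 0.826 = 0.42 at M1.

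- 1 October start, 1 February trough: m = -62. M4: 1.42 × sin(2π × (-2)/365.25) = -0.05. M1: 0.42 × sin(2π × (-47)/365.25) = -0.31.
- 30 November start, 1 January trough: m = 29. M4: 1.42 × sin(2π × 89/365.25) = 1.42. M1: 0.42 × sin(2π × 44/365.25) = 0.29.

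The drift in SDs is shift × amplitude. The last three columns give the chance of p<0.05 at M4 with no device effect, over both trough dates:

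| Start | M4 shift | Amplitude 0.1 SD | 0.2 SD | 0.4 SD |
|---|---|---|---|---|
| 1 October | -0.05 to 0.68 | 5-8% | 5-19% | 5-57% |
| 1 November | 0.68 to 1.22 | 8-16% | 19-48% | 57-97% |
| 30 November | 1.19 to 1.42 | 16-20% | 47-61% | 96-99% |

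At M1 the shift lies between -0.31 and 0.29 for every feasible start, and the corresponding chances are at most 6%, 8% and 16%. M4 is thus clearly more exposed for November starts. With a 1 October start and a 1 February trough the order reverses (0.05 against 0.31 in absolute size).

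**What a reference site would buy.** With equal SDs at the two sites and correlation ρ between their changes, the treated-minus-untreated difference has an SD of √(2(1-ρ)) times that of the single change. An effect of 0.355 SD has 80% power in the planned test. In the difference its power is 51%, 66%, 80% and 95% at ρ = 0, 0.3, 0.5 and 0.7. A drift common to both sites cancels; a drift specific to one site does not.

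**The case for a change.** The strongest case for a change is that an exploratory label does not turn change over time into effectiveness, and nothing in the synopsis limits how a significant result may be read. A caveat costs only words. A reading at an uninjected facial site uses probes and visits already planned, and as a supportive analysis it would take no power from the planned test. With a late start the exposure could be large. It also works in the other direction: an amplitude of 0.1 SD opposing a real effect of 0.355 SD leaves 0.355 - 0.142 = 0.213 to 0.355 - 0.119 = 0.236 SD, which is 39% to 46% power at M4.

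The limit on interpretation stands in full. The need for a change does not. The caveat restates what the endpoint already says and alters no estimate or test; a mean change with its 95% CI, described as change since D0, is how an analyst would normally report it. The reference site is a design preference. Dry skin is selected by a reading on the cheekbones, so another site need not share the same trend or the same regression towards the mean. It would add a procedure and eligibility or concomitant-treatment text for that site. The lack of a concurrent control is also not peculiar to these readings: it is a property of the declared single-arm design, and the GAIS endpoints share it.

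**Conclusion.** No change to the plan follows. The paired tests are valid for the endpoint they serve. They cannot by themselves attribute a change to the device, and the synopsis does not claim that they do. In this context the effectiveness heading separates these outcomes from the safety ones; it does not state a causal conclusion.

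The size of the possible bias is undetermined. Over feasible starts the assumed seasonal shift at M4 runs from about -0.05 to 1.42 amplitudes, and the chance of p<0.05 without a device effect runs from 5% to 99% for amplitudes of 0.1 to 0.4 SD. That range rests on an assumed cosine, trough date, amplitude and even enrolment, none of which is in the documents. The high figures belong to November starts, and the highest to the latest feasible one.

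Relying on D0 as the only comparator is a fair trade-off for secondary readings in an exploratory study, provided the results are read as change since D0. The primary GAIS analysis does not depend on them.
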